4.4.2. Main Analytical Approach

All exploratory endpoints will be summarised only.

Total hospital length and total intensive care length of stay will only be summarised if at least 10% of participants have one or more recorded event of interest. Length of stay will be summarised in all patients in the analysis set, in addition to those with the event of interest. Otherwise the data will be listed only.

4.5. Safety Analyses

The safety analyses will be based on the Safety Analysis Set, unless otherwise specified.

4.5.1. Extent of Exposure

Subjects will receive either an IV infusion of sotrovimab or a single IM injection of sotrovimab at one of two dose levels.

The intravenous sotrovimab dose will be 500 mg and will be infused over 15 minutes. The intramuscular sotrovimab dose will be either 250 mg or 500 mg given at a single timepoint. The 250 mg IM dose will be given either as a single 250 mg (4ml) injection in the dorsogluteal muscle or as two 2 ml injections in each deltoid muscle. The 500 mg IM dose will be administered as two 4 ml injections in each dorsogluteal muscle.

Summaries of exposure will be limited to the number of participants exposed and the number of participants with interruptions or infusions/injections stopped early and not completed.

4.5.2. Adverse Events

Adverse events analyses including the analysis of adverse events (AEs), Serious AEs (SAEs) and other significant AEs will be based on GSK Core Data Standards. As per the protocol, AEs are collected through Week 12 and SAEs collected through Week 36.

An overview summary of AEs will be produced, including counts and percentages of participants with:

- AEs
- AEs related to study intervention
- AEs leading to permanent discontinuation of study intervention,
- AEs leading to temporary interruption of study intervention
- Grade 3 and 4 AEs
- Grade 3 and 4 AEs related to study intervention,
- Grade 3 and 4 AEs leading to permanent discontinuation of study intervention,
- Grade 3 and 4 AEs leading to temporary interruption of study intervention
- SAEs
- SAEs related to study intervention,
- Fatal SAEs
- Fatal SAEs related to study intervention.
- Local infusion/injection site reactions

Adverse events will be coded using the latest version of the standard Medical Dictionary for Regulatory Affairs (MedDRA dictionary) and graded by the investigator according to the DAIDS 2017 v2.1.

The following adverse events will be considered of special interest (AESI) and will be summarised using frequency and percentages separately.

- Systemic infusion/injection related reactions (IRR) including hypersensitivity reactions (HSR); reactions within 24 hours of start of infusion will be identified using a list of MedDRA preferred terms confirmed by the Safety team.
- Local infusion/injection site reactions (ISR) will be identified using a list of MedDRA preferred terms confirmed by the Safety team.
- Immunogenicity (Anti-Drug Antibodies (ADA)) related adverse drug reactions will be reported. These potential events of ADAs will be detected by reviewing AEs that indicate HSR in those subjects who have positive anti-drug antibodies.
- Adverse events potentially related to antibody-dependent enhancement of disease (ADE) will be reported. These potential events of ADEs will be detected by reviewing adverse event/serious adverse events for an increase in the incidence and severity of COVID complications for a participant that cannot be explained by underlying risk factors.

In addition to the AE overview summary,

- Most common AEs defined as any AE preferred term (PT) with an incidence of at least $\geq 1\%$ (approx. 2 subjects) in any of the treatment group will be summarised using frequency and percentages separately.
- AEs by severity will be presented. The summary will use the following algorithms for counting the participant:
 - Preferred term row: Participants experiencing the same AE preferred term several times with different grades will only be counted once with the maximum grade.
 - Any event row: Each participant with at least one adverse event will be counted only once at the maximum grade no matter how many events they have.

The frequency and percentage of AEs (all grades) will be summarized and displayed in descending order by system organ class (SOC) and PT.

In the SOC row, the number of participants with multiple events under the same SOC will be counted once.

A separate summary will be provided for study intervention-related AEs. A study intervention-related AE is defined as an AE for which the investigator classifies the possible relationship to study intervention as “Yes”.

A worst-case scenario approach will be taken to handle missing relatedness data, i.e. the summary table will include events with the relationship to study intervention as ‘Yes’ or missing. The summary table will be displayed by PT only.

All SAEs will be tabulated based on the number and percentage of participants who experienced the event. Separate listings will also be provided for study intervention-related SAEs.

A study intervention-related SAE is defined as an SAE for which the investigator classifies the relationship to study intervention as “Yes”. A worst-case scenario approach will be taken to handle missing data, i.e. the summary table will include events with the relationship to study intervention as ‘Yes’ or missing.

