
VIR-7831  
Vir Biotechnology, Inc.

VIR-7831-5008 (GSK Study 217114)  
Amendment 4

Potential Risk of Clinical Significance	Summary of Data/Rationale for Risk	Mitigation Strategy
	
In the COMET-ICE study in participants with mild/moderate COVID-19 at high risk of progression, IRRs that occurred within 24 hours post infusion (pyrexia, chills, dizziness, dyspnea, pruritus, rash, and other infusion-related reaction) were reported in 6 (1%) of participants in the sotrovimab arm and 6 (1%) of participants in the placebo arm. All IRRs were nonserious, and Grade 1 or 2 severity and none led to treatment pausing or discontinuation. In the sotrovimab arm, all of the cases of IRRs were considered resolved and in the placebo arm, one participant had an event considered not resolved at the time of data cut-off. In COMET-ICE, all HSRs observed in the study were nonserious, of Grade 1 (mild) or Grade 2 (moderate) severity and reported in 2% of participants who received sotrovimab and in <1% who received placebo (9 participants treated with sotrovimab; 5 participants treated with placebo). None of the reactions in either arm led to pausing or discontinuation of the infusions. All events across both treatment groups were reported as resolved or resolving at the time of data cut-off.
 
No anaphylaxis events were reported in the COMET-ICE study in participants with mild to moderate COVID-19 not requiring hospitalization at study entry.
 
No anaphylaxis or serious hypersensitivity reactions were reported in the COMET-TAIL study in participants with mild to moderate COVID-19 not requiring hospitalization at study entry.
	
 
Investigational product will be administered in the clinic with staff trained in emergency care and resuscitation procedures with emergency care kit on hand during the study intervention administration and post-therapy observation periods.
 
Investigators will be instructed to discontinue IV infusions for participants who develop Grade 3 or higher infusion reactions.
 
If a participant experiences a Grade 2 IRR, investigators will be instructed to pause the infusion. The infusion may subsequently resume at a slower pace, at the investigator's discretion, and/or after symptomatic treatment (eg, antihistamines, IV fluids).
 
Infusion-related reactions including HSRs will be categorized as AESIs (as has been done in the past for other studies).
 

VIR-7831  

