### 3. OBJECTIVES AND ENDPOINTS

Objectives	Endpoints
Primary	
Safety Describe the safety and tolerability up through Day 8 of high dose ascending intravenous sotrovimab	
 
Occurrence of adverse events (AEs) through Day 8
 
Occurrence of serious adverse events (SAEs) through Day 8
 
Occurrence of adverse events of special interest (AESIs) through Day 8
 
Occurrence of disease related events (DREs) through Day 8
 

Secondary	
Safety Describe the safety and tolerability up through Week 36 of high dose ascending intravenous sotrovimab	
 
Occurrence of adverse events (AEs) through Week 12
 
Occurrence of serious adverse events (SAEs) through Week 36 (end of study)
 
Occurrence of adverse events of special interest (AESIs) through Week 12
 
Occurrence of disease related events (DREs) through Week 12
 

Safety Assess the immunogenicity up through Week 24 of high dose ascending intravenous sotrovimab	Incidence and titers (if applicable) of serum anti-drug antibody (ADA) and neutralizing antibody (if applicable) to sotrovimab through Week 24
Pharmacokinetics Assess the pharmacokinetics (PK) up to Week 24 of high dose ascending sotrovimab in serum following IV administration	IV sotrovimab pharmacokinetics (PK) in serum through Week 24
Exploratory	
Efficacy Evaluate the efficacy up through Day 29 of high dose ascending intravenous sotrovimab in preventing the progression of mild/moderate COVID-19	Progression of COVID-19 through Day 29 as defined by: 
 
Hospitalization > 24 hours for acute management of illness due to any cause
 
 OR 
 
Death
 

Efficacy Evaluate the efficacy up through Day 29 of high dose ascending intravenous sotrovimab in preventing the progression of mild/moderate COVID-19	Progression of COVID-19 through Day 29 as defined by: 
 
Visit to a hospital emergency room for management of illness
 
 OR

VIR-7831  
Vir Biotechnology, Inc.

VIR-7831-5008 (GSK Study 217114)  
Amendment 4

Objectives	Endpoints
	
 
Hospitalization for acute management of illness for any duration and for any cause
 
 
OR
 
 
Death
 

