#### **8.4.9. Adverse Events of Special Interest**

Adverse events of special interest are defined as relevant known toxicities of other therapeutic mAbs or are defined from signals observed in previous studies in the nonclinical or clinical sotrovimab programs, that the sponsor will monitor throughout the study. AESIs may be updated during the study based on accumulating safety data.

Adverse events of special interest include:

- Infusion-related reactions including hypersensitivity reactions within 24 hours after infusion
- Hypersensitivity reactions occurring at any time post dose
- Immunogenicity related AEs
- Adverse events potentially related to ADE of disease. Antibody-dependent enhancement theoretically can occur via 1 of 3 previously described mechanisms described in Section 8.4.9.3.

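### SAP 4.5.2 has no AESI row for hypersensitivity beyond 24 hours, which protocol 8.4.9 lists as its own AESI, and its 24-hour clock has no start for IM participants

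*SAP*

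**What the plan says.** Protocol Amendment 4, section 8.4.9, gives two separate hypersensitivity items among its AESIs: "Infusion-related reactions including hypersensitivity reactions within 24 hours after infusion" and "Hypersensitivity reactions occurring at any time post dose". The other two items are immunogenicity-related events and events potentially related to antibody-dependent enhancement (ADE).

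SAP version 2.0, section 4.5.2, has four AESI items:

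- systemic infusion or injection reactions, hypersensitivity included, with the clause "reactions within 24 hours of start of infusion will be identified using a list of MedDRA preferred terms confirmed by the Safety team";
- local site reactions;
- ADA-related reactions, found by "reviewing AEs that indicate HSR in those subjects who have positive anti-drug antibodies";
- ADE-related events.

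SAP 4.3.1.1 promises an overview count of participants with any AESI. The SAP version history bases version 2.0 on Amendment 3, and the SAP covers the IM versus IV study. Amendment 4 describes the high-dose IV substudy, and its section 9.4 promises a statistical analysis plan before Cohort A is formally reported.

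**The concern.** The SAP's only systemic hypersensitivity item carries a 24-hour limit. A reaction on Day 3 would then reach an AESI row only through the ADA item, so only if the participant is ADA-positive.

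AESI occurrence is a secondary endpoint of the main study. In the substudy it is a primary endpoint through Day 8 and a secondary one through Week 12 ("Occurrence of adverse events of special interest (AESIs) through Week 12"). If the 4.5.2 list were reused there, a 24-hour definition would cover one day of an eight-day or twelve-week endpoint.

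The clock raises a second question. The SAP item covers injections as well as infusions, but its clock starts at the start of infusion. IM participants have no infusion, and the main study compares IM with IV.

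**Working it through.** **1. The two lists against test cases (plain reading of the SAP)**

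| Systemic hypersensitivity reaction | Protocol 8.4.9 | SAP 4.5.2 |
|---|---|---|
| Within 24 h of an IV infusion | AESI | AESI |
| Day 3, ADA-positive | AESI (any-time item) | AESI (ADA item, no time limit) |
| Day 3, ADA-negative | AESI (any-time item) | no AESI row |
| 12 h after an IM injection | AESI (any-time item) | clock undefined |

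The local-reaction and ADE items do not cover the third case. That reaction is therefore also missing from the count of participants with any AESI.

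**2. What remains reported.** SAP 4.5.2 tabulates all AEs by system organ class and preferred term, by severity and by relatedness, and tabulates SAEs separately. The event is not lost. The grouped count is lost: hypersensitivity spreads over several preferred terms, and adding those rows does not give the number of participants with any such reaction.

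**3. Clock start.** The SAP counts from the start of infusion, the protocol from after infusion. If the latter means its end, the clocks differ by the infusion time: 15 minutes in the main study, 15 to 90 minutes in the substudy cohorts. This is small, but the two texts should agree.

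**4. Scale from COMET-ICE.** Protocol 2.3.1 reports infusion-related reactions within 24 hours in 6 participants per arm, and hypersensitivity in "9 participants treated with sotrovimab; 5 participants treated with placebo". Protocol 9.2 gives an infusion-related reaction rate of 1.14% and states a 90% chance of at least one event in 200 participants at that rate. The latter reproduces: 1 − (1 − 0.0114)^200 = 0.899.

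- Implied number treated with sotrovimab, taking 1.14% as that arm's rate: 6 / 0.0114 ≈ 526.
- Hypersensitivity rate: 9 / 526 = 1.7%.
- Assume that every hypersensitivity reaction within 24 hours was also counted among the 6. Then at least 9 − 6 = 3 fell outside the window, and at most 9 did. Rates: 3 / 526 = 0.57% to 9 / 526 = 1.71%.
- Expected in 340 participants: 1.9 to 5.8. Expected in 200: 1.1 to 3.4.
- Chance of at least one in 200 at 0.57%: 1 − (1 − 0.0057)^200 = 0.68.

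These are upper figures for what the AESI rows miss, since ADA-positive cases are still caught. Without the assumption the lower limit is 0, because onset times are not given.

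**5. The ADA item.** It sets no order in time between reaction and antibody. With 2% hypersensitivity, an assumed ADA positivity of 5% to 10%, and independence, chance overlap in an arm of 340 is 0.02 × 0.05 × 340 = 0.34 to 0.02 × 0.10 × 340 = 0.68 participants. This is a minor matter.

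**The case against.** **The lists belong to different versions.** The SAP is based on Amendment 3 for the IM versus IV study; the any-time item is in Amendment 4. A reader might infer that the SAP contradicts its own protocol. The documents do not show this: the Amendment 3 list is not supplied, the SAP has a local-reaction AESI that 8.4.9 lacks, and 8.4.9 allows AESIs to be updated. This objection stands.

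**The substudy has its own plan.** A reader might infer that the substudy's primary endpoint is already miscounted. That plan is not among the documents, so nothing shows that it omits the any-time item. Only the advice to carry the right definition into it remains.

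**The wording has a second reading.** The 24-hour clause follows a semicolon and may only say how acute reactions are identified. This is possible, but then delayed hypersensitivity has no stated method of identification. Either reading needs new text.

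**COMET-ICE does not isolate the window.** It is tempting to read 6 vs 6 against 9 vs 5 as proof that a longer window changes the message. The two pairs differ in event category as well as in window, so they cannot show that.

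**The ADA item is a review.** It describes potential events found by reviewing AEs, and timing can be weighed there. Counting only reactions from the first positive sample would do harm. In the Amendment 4 schedule, ADA is drawn pre-dose and next at about Day 29, so a true ADA-related reaction between Days 15 and 28 could precede the first positive sample and be removed.

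An argument that slower IM absorption makes 24 hours too short has no supporting data in the documents and is not made here.

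**Conclusion.** The point holds in limited form. SAP 4.5.2 has no row for hypersensitivity at any time post dose. On its plain reading, delayed reactions in ADA-negative participants are missed in the AESI rows and in the count of participants with any AESI. They remain in the general AE tables and, if serious, the SAE tables. The 24-hour clock is undefined for IM participants and differs from the protocol's.

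The likely size is a few participants per arm: about 2 to 6 in 340, or 1 to 3 in 200. This rests on the overlap assumption in step 4 of the working, on 1.14% being the sotrovimab-arm rate, and on COMET-ICE rates at 500 mg IV carrying over to other doses and routes. The true figure could be zero. No stated sample size or power figure changes. The reason to act is that the definition is incomplete and cheap to complete.

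**What to change.** In SAP 4.5.2:

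1. Add an AESI row for hypersensitivity reactions at any time post dose, with its preferred-term list, split into onset within 24 hours and later, and include it in the count of participants with any AESI.
2. Define the start of the 24-hour clock for both IV and IM, and align it with the protocol.
3. Keep every hypersensitivity reaction in ADA-positive participants in the ADA row, and only display its onset relative to the last negative and first positive sample.

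Use the same any-time definition and IV clock in the substudy SAP, where AESIs are primary through Day 8 and secondary through Week 12.

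The cost is SAP wording and one extra table row. No new data are needed, because AEs are already collected through Week 12 and SAEs through Week 36; after Week 12 the row can therefore hold only serious reactions. Amendment 4 already reports Day 29 results, so for the main study the row must be labelled as added after the Day 29 analysis.

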## 8.4. Adverse Events (AEs), Serious Adverse Events (SAEs) and Other Safety Reporting

The definitions of adverse events (AE) or serious adverse events (SAEs) can be found in [Section 10.3](#).

The definitions of unsolicited and solicited adverse events can be found in [Section 10.3](#).

AEs will be reported by the participant (or, when appropriate, by a caregiver, surrogate, or the participant's legally authorized representative).

Hospitalization or death are typically considered SAEs and they are included in the primary endpoint. However, if a hospitalization or adverse event is related to expected progression, signs, or symptoms of COVID-19 (as detailed in [Section 8.4.8](#)) or if hospitalization is due to elective treatment of a pre-existing condition that did not worsen from baseline as noted in [Section 10.3](#) it will not be considered as an SAE. These events will be collected and reported as SAEs only if the event is more severe than expected for the participant's current clinical status and medical history or if the investigator feels that it is related to study drug. These will be collected and reported as SAEs as delineated in [Section 8.4.1](#) below. Since it will not be possible to delineate in a single participant whether the hospitalization is directly related to COVID-19 complications or could be related to sotrovimab causing more severe disease due to ADE, all hospitalizations for management of acute illness, regardless of cause, will be included in the primary endpoint.

The investigator and any qualified designees are responsible for detecting, documenting, and reporting events that meet the definition of an AE or SAE and remain responsible for following up AEs that are serious, considered related to the study intervention or the study, or that caused the participant to discontinue the study (see [Section 7](#)). As noted in [Section 8.2.1](#) data on hospitalization or death should additionally be recorded in the eCRF for all relevant sections.

The method of recording, evaluating, and assessing causality of AEs and SAEs and the procedures for completing and transmitting SAE reports are provided in [Section 10.3](#).

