#### **8.4.8. Disease-Related Events and/or Disease-Related Outcomes Not Qualifying as AEs or SAEs**

Adverse events related to expected progression, signs, or symptoms of COVID-19, unless more severe than expected for the participant's current clinical status and medical history, or resulting in hospitalization as noted in Section 8.4, should not be reported as an AE or SAE.

However, if the underlying disease (i.e., progression) is greater than that which would normally be expected for the clinical course of the disease and/or the patient's clinical status, or if the investigator considers that there was a causal relationship between treatment with study treatment(s) or protocol design/procedures and the disease progression, then this must be reported as an AE or SAE.

For example, the following constitute events NOT meeting the AE definition and that should be considered as expected progression, signs, or symptoms of COVID-19:

- hypoxemia due to COVID-19 requiring supplemental oxygen
- hypoxemia due to COVID-19 requiring non-invasive ventilation or high flow oxygen devices
- respiratory failure due to COVID-19 requiring invasive mechanical ventilation or extracorporeal membrane oxygenation (ECMO)

**NOTE:** If either of the following conditions apply, then the event must be recorded and reported as an AE or SAE (instead of a disease-related event):

- The event is, in the investigator's opinion, of greater intensity, frequency, or duration than expected for the natural history of the disease, or
- The investigator considers that there is a reasonable possibility that the event was related to treatment with study treatment(s).

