#### 8.4.9.3. Antibody Dependent Enhancement

Antibody-dependent enhancement (ADE) of disease theoretically can occur via one of three previously described mechanisms:

1. By facilitating viral entry into host cells and enhancing viral replication in these cells
2. By increasing viral fusion with target host cells, enhancing viral replication in these cells
3. By enhancing disease pathology from viral antigen-antibody related immune complex deposition or complement activation and immune cell recruitment in target organs

The first two mechanisms are hypothesized to occur at sub-neutralizing antibody concentrations (Arvin 2020). This study will include participant follow-up for a period of 5 half-lives to assess for the potential of enhanced disease in the context of waning sotrovimab levels, which may manifest as an increased incidence of re-infection or increased severity of re-infections after recovery from initial illness. The third mechanism is hypothesized to occur at high levels of antigen (i.e., viral load) and antibody potentially leading to immune complex deposition and complement activation in tissue sites of high viral replication. This may manifest as acute deterioration temporally associated with sotrovimab dosing or as increased severity or duration of illness in sotrovimab-treated participants vs. placebo-treated participants.

As of 10 March 2021, enrollment into the COMET ICE study, evaluating sotrovimab for the treatment of non-hospitalized individuals with mild to moderate COVID-19, has been stopped based on the recommendation of IDMC. The total of 1057 participants have been randomized to either the IV infusion of sotrovimab Gen1 (500 mg dose) or placebo. Based on the Joint SRT review of blinded data, there has been no confirmed events of ADE. The ACTIV-3 TICO study of sotrovimab treatment in hospitalized participants with COVID-19 symptoms, which was terminated due to futility, did not reveal any safety concerns overall and no ADE. The COMET TAIL study did not reveal any safety concerns overall and no ADE.

As described in [Section 2.3.1](#), AEs potentially related to ADE of the disease will be reviewed by the JSRT to see if there are unusually severe manifestations of COVID-19 in treated individuals.

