4.3.1. Definition of Secondary Endpoints

4.3.1.1. Safety and tolerability

Adverse events analyses including the analysis of adverse events (AEs), serious AEs (SAEs) and other significant AEs will be based on GSK Core Data Standards.

An overview summary of AEs, including counts and percentages of participants with

- any AE
- any SAE
- any AESI

will be provided as outlined in Section 4.5.2. The Safety analysis set will be used.

Since it will not be possible to delineate in a single participant whether the hospitalization is directly related to COVID-19 complications or could be related to VIR-7831 causing more severe disease due to ADE, all hospitalizations regardless of cause will be included in the primary endpoint. However, if a hospitalization or adverse event is related to expected progression, signs, or symptoms of COVID-19 (as detailed in Section 8.4.8 of the Protocol) or if hospitalization is due to elective treatment of a pre-existing condition that did not worsen from baseline as noted in Section 10.3 of the Protocol it will not be considered as an SAE. These events will be collected and reported as SAEs only if the event is more severe than expected for the participant's current clinical status and medical history or if the investigator feels that it is related to study drug.

In addition, a summary of the number and percentage of participants with disease-related events, that is, events related to expected progression, signs, or symptoms of COVID-19, unless more severe than expected for the participant's current clinical status and medical history will be provided. These events will be captured on the disease related event CRF. This data will also be listed.

The following are examples of events NOT meeting the AE definition but will be classed and captured separately as disease progression events in the CRF:

- hypoxemia due to COVID-19 requiring supplemental oxygen
- hypoxemia due to COVID-19 requiring non-invasive ventilation or high flow oxygen devices
- respiratory failure due to COVID-19 requiring invasive mechanical ventilation or ECMO

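### The ADE review in SAP 4.5.2 uses only AE/SAE records, while COVID-19 deterioration judged expected goes to the disease-related event form, so the ADE count can be zero or too low

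*SAP*

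**What the plan says.** SAP 4.5.2 makes adverse events potentially related to ADE an adverse event of special interest (AESI) with its own summary. The detection rule is: "These potential events of ADEs will be detected by reviewing adverse event/serious adverse events for an increase in the incidence and severity of COVID complications". The judgement is made case by case, on an increase "for a participant that cannot be explained by underlying risk factors". Protocol 8.4.9.3 also works from AEs: "AEs potentially related to ADE of the disease will be reviewed by the JSRT" (the Joint Safety Review Team).

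Other sections decide what enters the AE/SAE records. On expected COVID-19 progression, Protocol 8.4.8 says "For example, the following constitute events NOT meeting the AE definition" and lists hypoxemia needing oxygen, then non-invasive ventilation or high-flow oxygen, then respiratory failure needing invasive ventilation or ECMO. SAP 4.3.1.1 gives the same list: "The following are examples of events NOT meeting the AE definition but will be classed and captured separately as disease progression events in the CRF". Protocol 8.4 and SAP 4.3.1.1 add that a hospitalization related to expected progression is not an SAE. An event returns to AE/SAE if the investigator considers it "of greater intensity, frequency, or duration than expected for the natural history of the disease", or sees a reasonable possibility that treatment caused it.

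On hospitalization, both documents accept that this judgement has a limit: "Since it will not be possible to delineate in a single participant whether the hospitalization is directly related to COVID-19 complications" or to ADE. For that reason they count all hospitalizations in the primary endpoint.

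**The concern.** The ADE rule looks for COVID-19 complications in records from which most expected COVID-19 complications have been routed away. A complication reaches the review only if the investigator has already judged it unexpected or possibly drug-related. For hospitalizations, the documents themselves say that the underlying cause cannot be determined in one participant. The risk-factor test narrows the review further: participants are enrolled because they are at high risk of progression, so an underlying explanation is nearly always available.

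ADE is a named risk in Protocol 2.3.1 and an AESI in Protocol 8.4.9. A report that no ADE events occurred would be read as the result of a search of the relevant cases. As written, the search may not have included them.

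**Working it through.** The plan gives no figure for ADE detection, so the main check is to trace where each event goes.

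| Event | Where it is recorded | Seen by the ADE review in SAP 4.5.2? |
|---|---|---|
| COVID-19 hypoxemia, ventilation or ECMO, judged expected | DRE form (Protocol 8.4.8, SAP 4.3.1.1) | No |
| COVID-19 hospitalization, judged expected | Not an SAE (Protocol 8.4, SAP 4.3.1.1); counted in the progression endpoint | No |
| Either, judged worse than expected or possibly related | AE/SAE | Yes |

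SAP 4.5.2.1 summarises DREs by treatment group, and SAP 4.3.1.1 adds counts, percentages and a listing. Neither section links DREs to the ADE review.

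**Illustration of size.** Inputs:
- 340 per arm, from SAP 5. The unpooled non-inferiority formula with 2% in both arms, a 3.5% margin, one-sided 2.5% and 90% power gives 337, so the planned number reproduces.
- Progression rates of 2.7% (500 mg IM) and 1.3% (500 mg IV), from the rationale in Protocol 1.1.
- q, the chance that a progression is both reported as an AE/SAE and flagged as ADE. The documents give no value, so a range is shown.

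Expected progressions are 340 × 0.027 = 9.2 and 340 × 0.013 = 4.4. In the arm with the higher rate, P(no ADE case) = (1 − 0.027q)^340.

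| q (assumed) | Expected ADE cases, 9.2 × q | P(no ADE case) |
|---|---|---|
| 0 | 0 | 100% |
| 0.02 | 0.18 | 83% |
| 0.05 | 0.46 | 63% |
| 0.10 | 0.92 | 40% |
| 0.20 | 1.84 | 16% |

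The calculation treats every progression as a candidate case. That is a simplification, because the endpoint counts hospitalization for any cause.

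**Conflicting text on hospitalization and death.** Protocol 8.4 and SAP 4.3.1.1 say that expected COVID-19 hospitalizations are not SAEs. Protocol 8.4.8 contains a clause that can be read as excepting events that lead to hospitalization. Protocol 8.2.1 lists the SAE form among the data to capture for a hospitalization or death, and Protocol 10.1.7 describes both as serious adverse events. Depending on which text a site follows, the same admission may or may not reach the ADE review.

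**The case against.** A reader might infer that an excess of severe COVID-19 in one arm would be hidden from the trial. The documents do not support that:
- All-cause hospitalizations are in the progression endpoint precisely because ADE and COVID-19 cannot be separated in one participant.
- DREs are summarised by treatment group.
- Severe or critical respiratory COVID-19 (SAP 4.3.1.4), ICU stay or ventilation (SAP 4.4.1.3) and changes in respiratory support (SAP 4.5.5) are all summarised.
- SAP 4.7 records that the JSRT noticed a discrepancy in hospitalization in the 250 mg IM arm, paused enrollment into it and escalated to the IDMC.

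The other side can also say that Protocol 8.4.8 sends unusual deterioration back to AE/SAE, and that this is the kind of case the ADE rule wants. Protocol 2.3.1 gives the JSRT wider material than AEs, including signs and symptoms, chemistry and end-organ disease.

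All of this stands, and it limits the point to the ADE AESI output. It does not close the gap. The return route depends on the investigator's prior suspicion, none of the arm-level outputs feeds the ADE count, and neither document names DREs as a source for the JSRT's ADE assessment.

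**Conclusion.** The point holds for the ADE AESI count. Followed as written, the rule can return zero or too few cases while candidate cases sit on the DRE and hospitalization forms. How often this happens depends on q, which the documents do not give. The count is certain to be zero only if every event is judged expected, which is an extreme assumption given the return route and the conflicting SAE text. This is a worthwhile correction of a safety output. It does not threaten the efficacy conclusions or the general safety monitoring.

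Two further inferences are tempting and should not be drawn. One is that ADE should be judged on arm-level rates. Every arm and cohort receives sotrovimab, so without placebo a difference cannot be told apart from lower efficacy of a dose or route. The other is that the SAP rule already applies to the safety substudy. SAP version 2.0 is based on Amendment 3, while the protocol supplied is Amendment 4. Protocol 9.4 says that the SAP will be finalized before formal reporting of Cohort A, and that substudy plan is not among the documents. In the substudy, DREs through Day 8 are themselves a primary endpoint (Protocol 3).

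**What to change.** 1. In SAP 4.5.2, define the sources for ADE case review as AEs, SAEs, DREs, all hospitalizations, respiratory-support escalations and deaths. Make Protocol 8.4.9.3 and the substudy SAP match.
2. State that classifying an event as expected progression does not remove it from that review.
3. Present the existing DRE and severity summaries by arm or cohort next to the ADE AESI table. Label them as context, not as a stand-alone ADE criterion.
4. Reconcile Protocol 8.4 and SAP 4.3.1.1 with Protocol 8.4.8, 8.2.1 and 10.1.7 on whether COVID-19 hospitalizations and deaths enter the SAE data.

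The cost is wording and table layout. The plan already provides for a DRE form and for recording hospitalization, oxygen, ventilation and death, so no new data collection is needed. The downside is a larger number of cases to review.
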